4.2 METHOD OF TREATMENT ASSIGNMENT AND BLINDING

This is an open-label study in which all patients will receive the 600-mg dose of ocrelizumab following the 24-week regimen. Therefore, no randomization or blinding will be used in this study.

4.3 STUDY TREATMENT

The investigational medicinal product (IMP) for this study is ocrelizumab.

4.3.1 Formulation, Packaging, and Handling

4.3.1.1 **Ocrelizumab**

Ocrelizumab will be supplied by the Sponsor as a liquid formulation containing 30-mg/mL ocrelizumab in 20 mM sodium acetate at pH 5.3, with 4% trehalose dihydrate and 0.02% polysorbate 20. The drug product is provided as a single-use liquid formulation in a 15-cc, type I USP, glass vial fitted with a 20-mm, fluoro-resin, laminated

Ocrelizumab—Genentech, Inc.
31/ Protocol MN30035, Version 5

stopper and an aluminum seal with a flip-off plastic cap and contains a nominal 300 mg ocrelizumab. No preservative is used as each vial is designed for single use.

The ocrelizumab drug product must be diluted before administration. Solutions of ocrelizumab for IV administration are prepared by dilution of the drug product into an infusion bag containing 0.9% sodium chloride to a final drug concentration of 1 to 2 mg/mL.

Ocrelizumab may contain fine translucent and/or reflective particles associated with enhanced opalescence. Do not use the solution if discolored or if the solution contains discrete foreign particulate matter.

The infusion solution must be administered using an infusion set with an in-line, sterile, non-pyrogenic, low-protein-binding filter (pore size of up to 0.2 micrometer).

The prepared infusion solution of ocrelizumab is physically and chemically stable for 24 hours at 2–8°C and subsequently 8 hours at room temperature. The prepared infusion solution should be used immediately. If not used immediately, it can be stored up to 24 hours at 2–8°C. Infusion solution must be completely administered to the patient within 32 hours of preparation (not exceeding 24 hours at 2–8°C and 8 hours at room temperature). In the event an IV infusion cannot be completed the same day, the remaining solution should be discarded.

For information on the formulation and handling of ocrelizumab, see the Ocrelizumab Investigator's Brochure.

4.3.2 Dosage, Administration, and Compliance

4.3.2.1 Ocrelizumab

Dose 1 of ocrelizumab will be administered as two 300-mg IV infusions (600 mg total) separated by 14 days (i.e., Days 1 and 15). Subsequent doses will be administered as one 600-mg IV infusion every 24 weeks for a maximum of 4 doses.

Although ocrelizumab may be administered on an outpatient basis, patients may be hospitalized for observation at the discretion of the investigator. Ocrelizumab infusions should always be administered in a hospital or clinic environment under close supervision of the investigator or a medically qualified staff member. It is anticipated that the patient will need to stay at the hospital or clinic for a full day for the infusion visits.

Each ocrelizumab infusion should be given as a slow IV infusion over approximately 150 minutes (2.5 hours) for the 300-mg dose and approximately 210 minutes (3.5 hours) for the 600-mg dose. To reduce potential IRRs, all patients will receive prophylactic treatment with 100 mg of methylprednisolone (or equivalent steroid), to be completed approximately 30 minutes before the start of each ocrelizumab infusion, and with an

Ocrelizumab—Genentech, Inc.
32/ Protocol MN30035, Version 5

antihistaminic drug (e.g., diphenhydramine) approximately 30–60 minutes before each ocrelizumab infusion.

Refer to Section 5.1.1 and Section 5.1.2 for the risks associated with these mandatory premedications.

It is also strongly recommended that the infusion is accompanied by prophylactic treatment with an analgesic/antipyretic such as acetaminophen/paracetamol (1 g) 30–60 minutes prior to the start of an infusion to reduce potential IRRs.

Since transient hypotension may occur during ocrelizumab infusion, the investigator may wish to withhold anti-hypertensive medications 12 hours prior to ocrelizumab infusion.

Ocrelizumab must not be administered as an IV push or bolus. Well-adjusted infusion pumps should be used to control the infusion rate, and ocrelizumab should be infused through a dedicated line. It is important not to use evacuated glass containers, which require vented administration sets, to prepare the infusion because this causes foaming as air bubbles pass through the solution.

After completion of the infusion, the IV cannula should remain in situ for at least 1 hour to allow for administration of drugs intravenously, if necessary, in the event of a delayed reaction. If no adverse events occur during this period of time, the IV cannula may be removed and the patient may be discharged.

See the Ocrelizumab Investigator's Brochure for detailed instructions on drug preparation, storage, and administration.

An overview of the ocrelizumab dosing is presented in Table 1.

Table 1 Overview of Ocrelizumab Dosing

Group	1 st Dose ^{a,c}		2 nd Dose ^{b,c}	3 rd Dose ^c	4 th Dose
	(Weeks 1–24)		(Weeks 24–48)	(Weeks 48–72)	(Weeks 72–96)
	Day 1 Infusion	Day 15 Infusion	Week 24 Infusion	Week 48 Infusion	Week 72 Infusion
Ocrelizumab	300 mg IV	300 mg IV	600 mg IV	600 mg IV	600 mg IV

IV=intravenous.

Note: Before each infusion of ocrelizumab, 100 mg of methylprednisolone IV and an antihistamine will be administered to reduce the potential for IRRs. Each treatment period has a duration of 24 weeks. The treatment period consists of *up to* 96 weeks of treatment; patients will receive a maximum of 4 treatment cycles.

^a The first dosing will consist of two IV infusions separated by 14 days (i.e., Days 1 and 15).

^b Beginning with the second dose, a single infusion of ocrelizumab will be administered.

^c Prior to the next infusion, a clinical evaluation will be performed to ensure that the patient remains eligible for retreatment.

Ocrelizumab—Genentech, Inc.
33/ Protocol MN30035, Version 5

Because of possible need to vary infusion rates depending on tolerance of the infusion, the total infusion time may exceed the time stated. **Unless an IRR occurs necessitating discontinuation, the entire contents of the infusion bag must be administered to the patient.**

Guidelines for treatment discontinuation are provided in Section [4.6.3](#).

Any overdose or incorrect administration of study drug should be noted on the Study Drug Administration electronic Case Report Form (eCRF). Adverse events associated with an overdose or incorrect administration of study drug should be recorded on the Adverse Event eCRF.

4.3.3 Mandatory Premedication: Methylprednisolone and Antihistaminic Drug

Premedicate with 100-mg methylprednisolone (or equivalent) completed approximately 30 minutes prior to each ocrelizumab infusion and with an antihistaminic drug (e.g., diphenhydramine) approximately 30 – 60 minutes before each infusion of ocrelizumab to reduce the frequency and severity of IRRs.

Any overdose or incorrect administration of methylprednisolone should be noted on the Pre-infusion Treatment eCRF. Adverse events associated with an overdose or incorrect administration of methylprednisolone or antihistamine should be recorded on the Adverse Event eCRF, with signs and symptoms also recorded on the dedicated Infusion-Related Reaction eCRF.

4.3.4 Other Prophylactic Treatment

The addition of an antipyretic (e.g., acetaminophen/paracetamol) may also be considered to further reduce the frequency and severity of IRRs.

4.3.5 Investigational Medicinal Product Accountability

All IMPs required for completion of this study (ocrelizumab) will be provided by the Sponsor. The study site will acknowledge receipt of IMPs, using the interactive voice/Web response system (IxRS) to confirm the shipment condition and content. Any damaged shipments will be replaced.

IMPs will either be disposed of at the study site according to the study site's institutional standard operating procedure or returned to the Sponsor with the appropriate documentation. The site's method of IMP destruction must be agreed to by the Sponsor. The site must obtain written authorization from the Sponsor before any unused IMP is destroyed, and IMP destruction must be documented on the appropriate form.

Accurate records of all IMPs received at, dispensed from, returned to, and disposed of by the study site should be recorded on the Drug Inventory Log.

Ocrelizumab—Genentech, Inc.
34/ Protocol MN30035, Version 5

4.3.6 Post-Trial Access to Ocrelizumab

Currently, the Sponsor (Genentech, a member of the Roche Group) does not have any plans to provide ocrelizumab or any other study treatments or interventions to patients who have completed the study, in accordance with the Roche Global Policy on Continued Access to Investigational Medicinal Product, available at the following Web site:

http://www.roche.com/policy_continued_access_to_investigational_medicines.pdf

4.4 CONCOMITANT THERAPY

Concomitant therapy includes any medication (e.g., prescription drugs, over-the-counter drugs, vaccines, herbal or homeopathic remedies, nutritional supplements) used by a patient from 4 weeks prior to screening to the study completion/ discontinuation visit. All such medications should be reported to the investigator and recorded on the Concomitant Medications eCRF.

Medications used after treatment discontinuation should be recorded during the Safety Follow-up Period (see [Appendix 1](#)).

4.4.1 Permitted Therapy

Patients who use oral contraceptives, hormone-replacement therapy, or other maintenance therapy should continue their use.

- Anti-hypertensive medications
 - Since transient hypotension may occur during ocrelizumab infusion, the investigator may wish to withhold anti-hypertensive medications 12 hours prior to ocrelizumab infusion.
- Corticosteroids
 - Patients who experience a relapse may receive treatment with IV or oral corticosteroids, if judged to be clinically appropriate by the investigator. Such patients should not discontinue study treatment solely based on the occurrence of a relapse, unless the patient or investigator feels he or she has met the criteria for withdrawal (Section [4.6.2](#)).

4.4.2 Prohibited Therapy

Use of the following therapies is prohibited during the program and for at least 7 days prior to initiation of ocrelizumab, unless otherwise specified below:

- Therapies for MS (see Section [4.1.2](#) for restrictions prior to initiation of ocrelizumab) other than systemic corticosteroids
- Immunosuppressants, lymphocyte-depleting agents, or lymphocyte-trafficking blockers while patient is B-cell depleted

See the Ocrelizumab Investigator's Brochure for a more detailed safety profile.

Ocrelizumab—Genentech, Inc.
35/ Protocol MN30035, Version 5

4.5 STUDY ASSESSMENTS

Please see [Appendix 1](#) for the schedule of activities to be performed during the study.

4.5.1 Informed Consent Forms and Screening Log

Written informed consent for participation in the study must be obtained before performing any study-related procedures. Informed Consent Forms for enrolled patients and for patients who are not subsequently enrolled will be maintained at the study site.

All screening evaluations must be completed and reviewed by the investigator to confirm that patients meet all eligibility criteria. The investigator will maintain a screening log to record details of all patients screened and to confirm eligibility or record reasons for screening failure, as applicable.

4.5.2 Medical History and Demographic Data

Medical history includes clinically significant diseases, surgeries, reproductive status, and all medications (e.g., prescription drugs, over-the-counter drugs, herbal or homeopathic remedies, nutritional supplements) used by the patient within 4 weeks prior to the screening visit. Demographic data will include age, sex, and self-reported race/ethnicity.

4.5.3 Physical Examinations

A full physical examination will be conducted at the screening and early termination visits. At all other visits, a limited physical examination will be conducted. Any abnormality identified at baseline should be recorded on the eCRF. Changes from baseline abnormalities should be recorded at each subsequent physical examination. New or worsened clinically significant abnormalities should be recorded as adverse events, if appropriate.

Height and weight will be measured at screening only. See [Appendix 1](#) (schedule of activities) for the timing of these assessments.

4.5.4 Neurological Examinations

Neurological examinations will be used to distinguish relapse in MS from another neurological (non-MS) disorder. Potential relapses should be recorded throughout the study. See [Appendix 1](#) (schedule of activities) for the timing of these assessments.

A protocol-defined relapse is an occurrence of new or worsening neurological symptoms attributable to MS. Symptoms must persist for >24 hours and should not be attributable to confounding clinical factors (e.g., fever, infection, injury, adverse reactions to medications) and immediately preceded by a stable or improving neurological state for least 30 days. The new or worsening neurological symptoms must be accompanied by objective neurological worsening consistent with an increase of at least half a step on the EDSS scale, or 2 points on one of the appropriate Functional Systems Score (FSS),

Ocrelizumab—Genentech, Inc.
36/ Protocol MN30035, Version 5

or 1 point on two or more of the appropriate FSS. The change must affect the selected FSS (i.e., pyramidal, ambulation, cerebellar, brainstem, sensory, or visual). Episodic spasms, sexual dysfunction, fatigue, mood change or bladder or bowel urgency or incontinence will not suffice to establish a relapse (Please note: Sexual dysfunction and fatigue need not be scored).

Investigators will also screen patients for signs and symptoms of worsening neurological function localized to the cerebral cortex, such as cortical symptoms/signs, behavioral and neuropsychological alteration, retrochiasmal visual defects, hemiparesis, and cerebellar symptoms/signs (e.g., gait abnormalities, limb incoordination). Patients with suspected PML should be withheld from ocrelizumab treatment until PML is ruled out by complete clinical evaluation and appropriate diagnostic testing (see [Appendix 6](#)). A patient with confirmed PML should be withdrawn from the study. PML should be reported as a serious adverse event (with all available information) with immediate notification of the Medical Monitor.

4.5.5 Vital Signs

Vital signs will include measurements of heart rate, temperature, and systolic and diastolic blood pressure.

Vital signs should be taken approximately 45 minutes prior to premedication. In addition, vital signs should be obtained prior to the ocrelizumab infusion and then approximately every 15 minutes for the first hour, followed by approximately every 30 minutes until 1 hour after the end of the infusion.

Patients will be informed about the possibility of delayed post-infusion symptoms and instructed to contact their study physician if they develop such symptoms.

4.5.6 Assessment of Disability

Disability in MS will be measured by the EDSS. See [Appendix 1](#) (schedule of activities) for the timing of these assessments. It is strongly recommended that the same EDSS rater is used for each patient throughout the study when possible. The EDSS should be done on the same day or within 24 hours prior to the study drug infusion if both are done at the same visit.

The EDSS is based on a standard neurological examination, incorporating seven functional systems (pyramidal, cerebellar, brainstem, sensory, bowel and bladder, visual, and cerebral [or mental], plus “other”) rated and scored as FSSs. Each FSS is an ordinal clinical rating scale ranging from 0 to 5 or 6. These ratings are then used in conjunction with observations and information concerning ambulation and use of assistive devices to determine the EDSS score. The EDSS is a disability scale that ranges in 0.5-point steps from 0 (normal) to 10 (death) (see [Appendix 3](#)).

Ocrelizumab—Genentech, Inc.
37/ Protocol MN30035, Version 5

Disability progression is defined as a \geq 1-point increase in EDSS score from baseline if the baseline EDSS score is between 0.0 and 5.5 (inclusive) or a 0.5-increase from baseline if the baseline EDSS score is higher than 5.5. The increase of disability progression on EDSS should be confirmed 24 weeks after the time at which the increase has been observed. The initial increase in EDSS can occur at any visit during the 96-week study.

4.5.7 Brain Magnetic Resonance Imaging

MRI will be used to monitor CNS lesions related to MS pathology and potentially other pathology findings. Brain MRI scans will be obtained at study visits as shown in the schedule of activities (see [Appendix 1](#)). The evaluation of scans for incidental pathology not related to MS, such as PML, is a local responsibility that should be handled according to the local practice. Any clinically significant findings should be reported on the Adverse Event eCRF.

MRI scans will be read by a centralized reading center for efficacy endpoints. Prior to initiation of treatment on Day 1/Baseline, a quality control (QC) report for the patients Screening MRI scan must have been received from the centralized reading center confirming scan passed QC. The brain MRI requires approximately 2 business days to be quality checked before dosing of ocrelizumab. Further details on scanning acquisition sequences, methods, handling, transmission of the scans, and certification of site MRI scanner are described in a separate MRI technical manual.

Assessments will include T1-weighted scans before and after injection of Gd contrast, and may also include, but may not be limited to: fluid-attenuated inversion-recovery (FLAIR), proton density-weighted, and T2-weighted scans.

4.5.8 Laboratory, Biomarker, and Other Biological Samples

Samples for the laboratory tests will collected on the days indicated in the schedule of activities (see [Appendix 1](#)).

Pre-infusion laboratory test results need to be available for review before each infusion, unless otherwise specified.

Routine safety laboratory assessments will include the following:

- Hematology (hemoglobin, hematocrit, RBCs, WBC absolute or differential, ANC, and quantitative platelet count)
- Serum chemistry (AST, ALT, GGT, total bilirubin, urea or BUN, uric acid, creatinine, potassium, sodium, calcium, and phosphorus)
- Urinalysis or urine dipstick on site (standard to assess kidney function)
- Pregnancy test
 - All women of childbearing potential will have a serum or urine pregnancy test at screening. Urine pregnancy tests will be performed at specified subsequent

Ocrelizumab—Genentech, Inc.
38/ Protocol MN30035, Version 5

visits. If a urine pregnancy test is positive, it must be confirmed by a serum pregnancy test.

- Viral serology and detection:
 - Hepatitis B (HBsAg and HBcAb confirmed, if positive, by positive viral DNA PCR)
 - For enrolled patients with negative HBsAg and positive total HBcAb, hepatitis B virus (HBV) DNA (by PCR) must be repeated every 24 weeks
 - Hepatitis C virus (HCV) antibody (performed only at screening)

Additional samples will include the following:

- Lymphocyte subtypes
 - Whole-blood samples will be collected to determine the duration of B-cell depletion and recovery (CD19+) and T-cell counts (CD4+, CD8+).

Per local Institutional Review Board (IRB)/Ethics Committees (ECs) requirements, additional testing may be required for selected patients or selected centers to exclude TB, Lyme disease, HTLV-1 associated myelopathy (HAM), AIDS, hereditary disorders, connective tissue disorders, or sarcoidosis.

4.5.9 Patient-Reported Outcomes

PRO data will be elicited from patients in this study to better characterize patient quality of life and treatment satisfaction while on ocrelizumab. PROs completed at baseline should be in reference to the last-used DMT prior to enrollment.

The Multiple Sclerosis Impact Scale (MSIS-29) is a 29-item questionnaire designed to measure the physical and psychological impact of MS from the patient's perspective. Additionally, the Treatment Satisfaction Questionnaire for Medication (TSQM II) and the Treatment Satisfaction with Medicines Questionnaire (SATMED-Q), questionnaires to assess patients' treatment satisfaction, will be administered to patients during the visits listed in the schedule of activities (see [Appendix 1](#)).

Please note that all PROs are required to be administered prior to administration of study drug and prior to any other study assessment(s) to ensure the validity of the instruments is not compromised. Also note that the methods for collecting and analyzing PRO data are different from those for the ascertainment of observed or volunteered adverse events. Due to these differences, PRO data will not be reported as adverse events and no attempt will be made to resolve any noticeable discrepancies between PRO data and observed or volunteered adverse events.

4.5.10 Safety Follow-up Period

Patients who complete *their infusion at Week 72* or who discontinue from treatment early should enter the Safety Follow-up Period and be assessed *at 24 weeks*. *If the peripheral blood B-cell count remains depleted after 6 months from the date of the last*

Ocrelizumab—Genentech, Inc.
39/ Protocol MN30035, Version 5

infusion, the investigator may want to continue monitoring the B-cell count until it has returned to the baseline value or to the lower limit of the normal range, whichever is lower. During the Safety Follow-Up Period, patients who receive other B-cell targeted therapies will only be followed for an additional period of approximately 24 weeks from the start of the alternative MS treatment.

See [Figure 2](#) for an overview of the Safety Follow-up Period and [Appendix 1](#) for the schedule of activities.

4.6 PATIENT, TREATMENT, STUDY, AND SITE DISCONTINUATION

4.6.1 Patient Discontinuation

Patients have the right to voluntarily withdraw from the study at any time for any reason. In addition, the investigator has the right to withdraw a patient from the study at any time. Reasons for withdrawal from the study may include, but are not limited to, the following:

- Patient withdrawal of consent at any time
- Any medical condition that the investigator or Sponsor determines may jeopardize the patient's safety if he or she continues in the study
- Investigator or Sponsor determines it is in the best interest of the patient
- Patient non-compliance, defined as failure to follow dosing instructions or to complete program visits

Every effort should be made to obtain information on patients who withdraw from the study. The primary reason for withdrawal from the study should be documented on the appropriate eCRF. However, patients will not be followed for any reason after consent has been withdrawn. Patients who withdraw from the study will not be replaced.

4.6.2 Criteria for Re-Treatment with Ocrelizumab

Prior to re-treatment with ocrelizumab, patients will be evaluated for the following conditions and laboratory abnormalities. If any of these are present prior to re-dosing, further administration of ocrelizumab should be suspended until these are resolved or held indefinitely:

- Life-threatening (Grade 4) infusion-related event that occurred during a previous ocrelizumab infusion
- Any significant or uncontrolled medical condition or treatment-emergent, clinically significant laboratory abnormality
- Active infection
- Ongoing pregnancy *or breastfeeding*

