4.6.3 Study Treatment Discontinuation

Patients must discontinue study treatment if they experience any of the following:

- Life-threatening IRR or serious hypersensitivity reaction

Ocrelizumab—Genentech, Inc.
40/ Protocol MN30035, Version 5

- Active hepatitis B infection
- PML
- Active TB, either new onset or reactivation

The primary reason for study treatment discontinuation should be documented on the appropriate eCRF. Patients who discontinue study treatment prematurely will not be replaced.

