5.1.4 Management of Patients Who Experience Specific Adverse Events

Guidelines for management of specific adverse events are outlined in [Table 2](#). Additional guidelines are provided in the subsections below.

Table 2 Guidelines for Management of Specific Adverse Events

Event	Action to Be Taken
Mild to moderate IRR	
• If the event that a patient experiences is a mild to moderate IRR (e.g. headache), the infusion rate should be reduced to half the rate at the time of the event.• This reduced rate should be maintained for at least 30 minutes. If tolerated, the infusion rate may then be increased according to the patient's initial infusion schedule.
Severe IRR (or complex of flushing, fever, and throat pain)	
• If a patient experiences a severe IRR or a complex of flushing, fever, and throat pain symptoms, the infusion should be interrupted immediately and the patient should receive symptomatic treatment.• The infusion should be restarted only after all symptoms have resolved.• The initial infusion rate at restart should be half of the infusion rate at the time of onset of the reaction.

Event	Action to Be Taken
Life-threatening or disabling IRR (e.g., anaphylaxis)	
 Immediately stop ocrelizumab if there are signs of a life-threatening or disabling IRR during an infusion, such as acute hypersensitivity or acute respiratory distress syndrome. The patient should receive appropriate treatment. Permanently discontinue ocrelizumab in these patients.

IRR = infusion-related reaction.

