Appendix 2 ***Optional Shorter Infusion Substudy (cont.)***

OBJECTIVES

The primary objective of this study is to evaluate the rate and severity of infusion-related reactions (IRRs) of the ocrelizumab 600-mg infusion administered over the course of 2 hours, instead of the currently approved duration of 3.5 hours, in patients with MS who have had prior treatment with ocrelizumab in MN30035 (CHORDS), as measured by the rate and frequency of National Cancer Institute Common Terminology Criteria for Adverse Events, Version 4.0 (NCI CTCAE v4.0) Grade 3 and 4 IRRs.

STUDY DESIGN

This is an open-label, non-randomized substudy to MN30035 designed to evaluate the safety and tolerability of ocrelizumab infused over a shorter time period than the approved administration rate. Patients who complete their Week 72 ocrelizumab infusion and do not experience any serious IRR (see Section 5.2.2 for seriousness criteria) throughout the main study will be eligible to enroll in this optional substudy and receive one additional shorter infusion of ocrelizumab at the Week 96 visit.

Premedication in the substudy will be administered per the main study methods (Section 4.3.3). Ocrelizumab will then be administered as a single 600-mg dose at a shorter infusion rate (i.e., over the course of approximately 2 hours instead of 3.5 hours) than in the main study.

Ocrelizumab infusion rate will be slowed and/or stopped if a patient experiences a Grade 3 or higher IRR or other serious adverse event.

Patients who received ocrelizumab at a shorter infusion rate at the Week 96 visit will return for a substudy follow-up visit approximately 30 days after treatment.

The end of the treatment period in the substudy is defined as the date when the last patient in the substudy completes the substudy follow-up visit (Week 100).

Planned Total Sample Size

This substudy will enroll approximately 100 patients from MN30035 who did not experience any serious IRR throughout the main study.

OUTCOME MEASURES

Safety Outcome Measures

- *Rate and frequency of Grade 3 or 4 IRRs with onset on or after the shorter ocrelizumab infusion at Week 96 and at the substudy follow-up*
- *Changes in physical findings and vital signs with onset on or after the shorter ocrelizumab infusion at Week 96 and at the substudy follow-up*

Ocrelizumab—Genentech, Inc.
80/ Protocol MN30035, Version 5

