Appendix 2 **Optional Shorter Infusion Substudy (cont.)**

require vented administration sets, to prepare the infusion because this causes foaming as air bubbles pass through the solution.

After completion of the infusion, the IV cannula should remain in situ for at least 1 hour to allow for administration of drugs intravenously, if necessary, in the event of a delayed reaction. If no adverse events occur during this period of time, the IV cannula may be removed and the patient may be discharged.

See the Ocrelizumab IB for detailed instructions on drug preparation, storage, and approved administration.

Dosage Modification

Unless an IRR occurs necessitating discontinuation, the entire contents of the infusion bag must be administered to the patient.

Patients must discontinue study treatment if they experience any of the following:

- *Life-threatening IRR or serious hypersensitivity reaction*
- *Active hepatitis B infection*
- *Progressive multifocal leukoencephalopathy (PML)*
- *Active tuberculosis, either new onset or reactivation*

SUBSTUDY ASSESSMENTS

Substudy assessments will be performed according to the schedule of activities in Table 3.

Informed Consent Forms and Screening Log

Written informed consent for participation in the substudy must be obtained before performing any substudy-related procedures.

Physical Examinations

A limited physical examination will be conducted at the substudy treatment visit. Any abnormality identified prior to treatment administration in the substudy should be recorded on the eCRF. New or worsened clinically significant abnormalities after treatment administration should be recorded as adverse events, if appropriate.

Vital Signs

Vital signs will include measurements of heart rate, temperature, and systolic and diastolic blood pressure.

Ocrelizumab—Genentech, Inc.
83/ Protocol MN30035, Version 5

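### The substudy's infusion rule lets sites answer a Grade 3 or higher infusion-related reaction by slowing alone, which conflicts with Section 5.1.4, Table 2

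*Protocol*

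**What the plan says.** Section 5.1.4, Table 2 sets three tiers of action for an IRR.

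- Mild to moderate: halve the rate, hold it there for at least 30 minutes, then increase if tolerated.
- Severe, or the combination of flushing, fever and throat pain: "the infusion should be interrupted immediately and the patient should receive symptomatic treatment". Restart is allowed only when every symptom has gone, at half the earlier rate.
- Life-threatening or disabling: "Immediately stop ocrelizumab if there are signs of a life-threatening or disabling IRR during an infusion", followed by "Permanently discontinue ocrelizumab in these patients".

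The substudy gives 600 mg over about 2 hours instead of 3.5. The Study Design text of Protocol Appendix 2 has its own rule: "Ocrelizumab infusion rate will be slowed and/or stopped if a patient experiences a Grade 3 or higher IRR or other serious adverse event". SAP Appendix 6 (Substudy Design) repeats it. Under Dosage Modification, Appendix 2 also lists reasons for mandatory discontinuation, the first being "Life-threatening IRR or serious hypersensitivity reaction".

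In the main study, Section 4.6.3 opens with "Patients must discontinue study treatment if they experience any of the following" and begins with the same first item. Section 4.6.2, on re-treatment, lists "Life-threatening (Grade 4) infusion-related event that occurred during a previous ocrelizumab infusion" beside active infection, pregnancy and breastfeeding. Its instruction for all of them is that "further administration of ocrelizumab should be suspended until these are resolved or held indefinitely".

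**The concern.** The same reaction meets rules of different strength depending on which page the site reads. The difference matters most in the substudy. The infusion is faster there, Grade 3 and 4 IRRs are the main outcome, and the local sentence names a weaker permissible action than the protocol's management table. A site that only slows the pump for a severe reaction complies with Appendix 2 but not with Table 2.

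Two further differences point the same way. Table 2 requires a permanent stop for a disabling IRR, yet neither mandatory list names one. Section 4.6.2 groups a past Grade 4 reaction with conditions that resolve. What is at stake is clear dosing-safety instructions; the efficacy estimate is not involved.

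**Working it through.** No arithmetic applies. The check sets trigger and action side by side.

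| Reaction | Section 5.1.4, Table 2 | Appendix 2 Study Design; SAP Appendix 6 | Mandatory lists (4.6.3; Appendix 2 Dosage Modification) | Section 4.6.2 |
|---|---|---|---|---|
| Severe (Grade 3) | Interrupt at once; restart at half rate after full resolution | Slowing alone is enough | Not listed | Not listed |
| Life-threatening (Grade 4) | Stop; permanent discontinuation | Slowing alone is enough, read by itself | Must discontinue | Suspend until resolved, or hold indefinitely |
| Disabling, not life-threatening | Stop; permanent discontinuation | Slowing alone is enough, if Grade 3 or higher | Not named | Not named |

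**Severe row.** The conflict is direct, and nothing else in Appendix 2 removes it. The Dosage Modification list corrects the Study Design sentence for life-threatening reactions only. Appendix 2 cites Sections 4.3.3 and 5.2.2 but never 5.1.4, and its own Table 2 is the sample-size table. The SAP's substudy exposure summary treats slowing, interrupting and stopping as distinct interventions, yet the rule does not mention interruption.

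**Matching Grade 3 to severe.** Section 5.3.3, Table 3 labels Grade 2 moderate and Grade 3 severe. That scale is for events not listed in the CTCAE, so applying it to IRRs is an assumption. It is the only mapping the documents give.

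**Life-threatening row.** Section 4.6.3 and the Appendix 2 list both compel discontinuation, in agreement with Table 2. The looser lines conflict with a binding rule but do not displace it.

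**Disabling row.** Table 3 places disabling events in Grade 3, below life-threatening, so the one term does not cover the other. The gap is narrowed in two ways. Both lists include serious hypersensitivity, and Section 5.2.2 counts significant disability as a seriousness criterion. Section 5.1.3.2.3 also requires an immediate and permanent stop whenever hypersensitivity is suspected during an infusion. What remains unlisted is a disabling IRR that is neither life-threatening nor hypersensitivity.

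**The case against.** The best defence is that the substudy sentence is a design summary. It also covers other serious adverse events, which explains its breadth, and slowing and stopping together could be shorthand for interrupting and then restarting at half rate. The Appendix 2 Safety Plan relies on interruption criteria specified in the protocol, and Table 2 supplies these for IRRs. It also refers sites to the Investigator's Brochure for managing specific events. The substudy is a single infusion in about 100 patients with no earlier serious IRR.

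This lowers the severity but does not remove the conflict. Read literally, the sentence permits slowing alone. The Safety Plan names no section for its criteria, and the Brochure is not among the documents.

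On the other two points the defence largely succeeds. A patient with a life-threatening IRR is already off treatment under Section 4.6.3 before any re-treatment check, and Section 4.6.2 itself offers an indefinite hold. For disabling reactions, Table 2 is a direct instruction in the main study, its examples for that tier are mainly of the hypersensitivity type, and the provisions noted above cover most cases.

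A reader might infer from Section 4.6.2 that the protocol allows re-dosing after a Grade 4 reaction. Read with Section 4.6.3 and Table 2, it does not.

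**Conclusion.** The substudy rule should be corrected. For a severe IRR it permits a weaker action than Section 5.1.4, Table 2, and nothing else in Appendix 2 resolves the difference. This rests on matching Grade 3 to severe, as Table 3 does. The omission of disabling IRRs from the two lists is real but narrow, and the Section 4.6.2 wording is a consistency matter only.

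Severity is low, and the primary analysis is not affected. No numerical size is claimed. A reader might try to derive one from the single Grade 4 serious IRR with ocrelizumab in the pooled relapsing-MS studies (Section 1.2.1.2), or from the substudy planning table of 1 to 7 patients with Grade 3 or 4 IRRs in 100. Those figures count reactions, not reactions handled wrongly, and a Grade 4 reaction already falls under a binding stop rule. Nor can a dose consequence be stated. The substudy sentence does not say by how much or for how long to slow, and because Table 2 allows restart after a severe IRR, any assumed slowing would show timing only.

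**What to change.** **Main change.** In Protocol Appendix 2, Study Design, replace the IRR part of the sentence with:

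*IRRs are managed per Section 5.1.4, Table 2. Severe (Grade 3) IRR, or flushing, fever and throat pain together: interrupt at once, treat, and restart at half rate only when all symptoms are gone. Life-threatening or disabling IRR, whatever its grade: stop and permanently discontinue.*

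Keep a separate rule for other serious adverse events with the present slow-or-stop options. Use the same wording in SAP Appendix 6. Cite the section number, because Appendix 2 has a different Table 2. The phrase *whatever its grade* is needed because a disabling reaction can be Grade 3 and would otherwise meet both lines.

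**Secondary alignment.** Add *or disabling* after *Life-threatening* in the first item of Section 4.6.3 and of the Appendix 2 Dosage Modification list. Have the Grade 4 bullet in Section 4.6.2 refer to Section 4.6.3. Table 2 of Section 5.1.4 stays as it is.

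**Cost.** Four short protocol edits (4.6.2, 4.6.3 and two in Appendix 2) and one SAP passage at the next amendment, with a letter to sites in the meantime if wanted. There is no data or analysis cost.
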